1. CLINICAL STUDY INFORMATION

1.1 Background

Fluoride toothpaste is the most widely used form of fluoride delivery worldwide. Fluoride dentifrices have shown in numerous clinical trials to be effective anticaries agents and have been the subject of several systematic quantitative evaluations (Marinho et al., 2003; Twetman et al., 2003), which provide the highest standard of evidence for the effectiveness of fluoride dentifrice. Marinho et al. (2003) based their conclusions on a meta-analysis of 70 trials of the effectiveness of fluoride dentifrice for the prevention of dental caries in children compared to placebo. They found evidence that the use of fluoride dentifrices has a caries-inhibiting effect (average reduction in Decay, Missing, and Filled Surfaces (DMFS) of 24%) on the permanent dentition. In addition, they concluded that the effectiveness of fluoride dentifrice may be relatively greater in individuals with a higher caries experience, with increased fluoride concentration, increased frequency of use, and with supervised brushing. There was no evidence that the effect was dependent on background exposure to fluoridated water. Twetman et al. (2003) reached similar overall conclusions from their systematic review.

The current levels of fluoride dentifrice products that are marketed worldwide generally fall in the range between 1000 – 1500 ppm F, although dentifrices with lower fluoride concentrations are marketed in some countries. All fluoride toothpaste sold in the US is in the 1000-1100 ppm F range. Walsh et al. (2010) reported based on a network meta-analysis that the relative anticaries effects of fluoride toothpastes increased with higher fluoride concentration. Based on 74 trials involving the caries scores (DMFS) in the mixed or permanent dentition, the anticaries effect of fluoride toothpaste was 23% for 1000/1055/1100/1250 ppm F and 36% 2400/2500/2800 ppm F; however, toothpastes with 440/500/550 ppm F and below did not show a statistically significant effect compared to placebo.

Clinical caries trials remain the standard for evaluating the safety and efficacy of fluoride dentifrice products. However, due to the high cost involved in conducting clinical caries trials, several surrogate measures of fluoride efficacy have been introduced. These include in situ caries models, rat caries models, in vitro demineralization and remineralization studies, and fluoride uptake studies. These model systems have been extensively reviewed at a Conference held in Rochester, NY in 1994 (Adv Dent Res 9:169-340, 1995). While intra-oral models have been in use for the past forty years, a "Consensus Conference of Intraoral Models" (ADA, Chicago, Sept. 1990) clearly identified the need for validation of intra-oral caries models for their potential use as methods of evaluating the efficacy of fluoride dentifrices and other fluoride-containing dental products. Based on this conference and the Rochester Models conference, there is general agreement among researchers in the field that appropriately validated in situ models represent an acceptable approach for testing the anticaries potential of fluoride products. The use of intra-oral appliance models overcome the ethical and practical problems associated with human studies by permitting the evaluation of subtle changes in the mineral status of enamel specimens occurring at a well-controlled test site mounted in the subject's own partial denture. Intraoral models serve as bridges between the clinical situation and the more controlled laboratory environment. Philosophically, these models should, as far as possible, be representative of what occurs in the clinical situation, yet keep variables under control so that meaningful outcome differences can be detected in a reasonable number of subjects (Zero, 1995).

Previous work by our group has shown that a modification of the Koulourides intra-oral model (Koulourides et al., 1974) has sufficient sensitivity and reproducibility to respond in dose-response manner to meet the requirements for model validation (Proskin et al., 1992). The model, which uses partially demineralized enamel as the starting hard tissue substrate, permits the evaluation of the ability of the test dentifrice to enhance net remineralization and measure fluoride bioavailability under clinically relevant conditions. Our current model has been validated based on its response to different dentifrice fluoride concentrations - 0, 250, 500 and 1100 ppm fluoride (Zero et al., 1994; Zero, 1995; Zero et al., 2005) as well as in several more commercially funded in situ studies testing fluoride dentifrice products that also included fluoride dose response controls (Zero et al., 2018).

Our intraoral model system uses the surface microhardness (SMH) test to assess changes in the mineral content of enamel. A very precise instrument (Wilson 2100 Hardness Tester) with a Knoop diamond under a fixed load is used to place indentations into the enamel surface. The length of the indentations is accurately measured using an image analysis system and correspond directly to the depth of

penetration of the diamond into the enamel surface (30:1 ratio). This method can be considered analogous to the dentist's use of a sharp dental probe to detect clinical dental caries; however, the SMH test is hundreds-fold more sensitive and accurate. Using the SMH test, the hardness of sound enamel can be measured and compared with the hardness of enamel after exposure to a caries (demineralization) challenge and after exposure to conditions that favor remineralization. An increase in the indentation length compared to the baseline indentation length indicates softening of the enamel and demineralization. A decrease in the indentation length represents rehardening of the enamel surface and remineralization. The SMH test is one of the few methods that can be used to accurately determine the very early changes occurring at the enamel surface during the caries process (Zero, 1995). For early enamel lesions, a decrease in SMH has been shown to be linearly related to mineral loss (demineralization) (Zero et al., 1990). White (1988) reported that for shallow enamel lesions, an increase in SMH was highly correlated with remineralization as measured by microradiography.

Another advantage of our in-situ model system is that fluoride uptake can be measured on the same enamel specimens that are used to evaluate changes in mineral status (demineralization/remineralization) of enamel. Fluoride uptake testing using in vitro models is accepted by the American Dental Association as one of the profile methods for generic efficacy testing of dentifrices in their Seal Acceptance Program and by the Food and Drug Administration as one of the testing procedures for fluoride dentifrice drug products in the Final Monograph - Anticaries Drug Products for Over-the-Counter Human Use. An important advantage of determining F uptake using an intraoral appliance model is that studies are conducted under clinically relevant conditions, which very closely approximate the in vivo situation. Human subjects apply the test dentifrice by brushing their teeth during the intraoral study. The fluoride is delivered in the presence of physiologically secreted saliva and there are intermittent cycles of demineralization and remineralization during the experimental period as with the natural caries process. Furthermore, when the active fluoride agent in a dentifrice is sodium monofluorophosphate (MFP), plaque and saliva present in the oral environment provide the necessary phosphatases to hydrolyze MFP to release free fluoride ion (Pearce and Dibdin, 1995). This will take place only to a limited extent when using non-biologic in vitro testing methods. Thus, the determination of intraoral fluoride uptake should provide a better estimation of the true fluoride bioavailability of fluoride dentifrice products than determination of fluoride uptake in vitro.

1.2 Investigational Products

- 0 ppm F toothpaste and Oral-B® Indicator soft toothbrush.
- 250 ppm F sodium monofluorophosphate toothpaste and Oral-B® Indicator soft toothbrush.
- 1100 ppm F sodium monofluorophosphate toothpaste and Oral-B® Indicator soft toothbrush.
- 2800 ppm F sodium monofluorophosphate toothpaste and Oral-B® Indicator soft toothbrush.
- 1100 ppm gluconate-stabilized SnF₂ toothpaste and Oral-B® Indicator soft toothbrush.

1.3 Summary of Findings

Previous in-situ caries model dose response studies have evaluated the dose response of different dentifrice fluoride concentrations through the use of this in situ caries model.

1.4 Known Potential Risks and Benefits

This study is for research purposes only. There may be no direct benefit to the subjects from participation in the study. Others may benefit from the knowledge gained. There may be other risks of study participation that are unknown. There is no guarantee that the subjects will receive any medical or dental benefits from participating in this research study.

1.5 Investigational Product Dosage

Each subject will be randomized to each of the treatment groups below:

- 0 ppm F toothpaste
- 250 ppm F sodium monofluorophosphate toothpaste

- 1100 ppm F sodium monofluorophosphate toothpaste
- 2800 ppm F sodium monofluorophosphate toothpaste

Subjects willing to participate in a fifth leg of the study will receive 1100 ppm gluconate-stabilized SnF₂ toothpaste as the investigational product.

Subjects will be instructed to brush twice daily (morning and at bedtime) with their assigned dentifrice for 21 days following the brushing instructions found in the Appendix. Subjects will be instructed to brush the biting surfaces of their back teeth (but not enamel specimens) with a full ribbon of study dentifrice for one timed minute while wearing their partial dentures, followed by rinsing with the 15 mL of measured tap water for 10 seconds and then expectorating. Subjects who are regular floss users will be allowed to continue flossing; use of any non-study related products will be disallowed. Compliance with brushing procedures will be recorded in subject diaries (see Appendix), as well as any *de novo* or changes in medical conditions, medications or treatments.

1.6 Ethical Compliance

Prior to study initiation, the Investigator must obtain institutional review and approval of the Protocol, the consent form, and other necessary study-related documents in compliance with the US Code of Federal Regulations, Title 21, Part 56 or the ICH-GCP Consolidated Guidelines, Chapter 3 and in compliance with Procter & Gamble SOP CTN-CL-504 ("Institutional Review Board/Independent Ethics Committee Review and Approval"). The Investigator will maintain any original authorization letter(s) and will be available for review by the Sponsor. IRB approval letters should include the study title, Sponsor study number, the address of the IRB, date of request, and the signature of the IRB chairperson or designate. Additionally, the letter must acknowledge that both the Protocol and consent form have been approved by the IRB. The study will not begin until the Sponsor has received confirmation of IRB approval. The IRB shall also review the investigation at least once a year during study execution. The Investigator will notify the IRB when the study is terminated and provide confirmation that the study has been closed with the IRB to the Sponsor.

The Investigator will obtain written informed consent for each subject prior to participation in the study, per the US Code of Federal Regulations, Title 21, Parts 50.25 and 50.27 and ICH-GCP, Chapter 4, subpart 4.8 and in compliance with Procter & Gamble SOP CTN-CL-503 ("Informed Consent Form, Ethics Approval and Investigator Use"). Subjects, or their legal guardian, are required to read, sign and date an IRB approved consent form with the Investigator also maintaining a signed and dated copy. The subject or legal guardian will be given a copy of the consent form. All study procedures must be explained in non-technical terms.

Changes to the Protocol following IRB approval affecting the safety of subjects, scope or objectives of the investigation, or the scientific quality of the study will be documented as amendments. Such changes will require the Sponsor, Investigator, and IRB approval prior to implementation, unless immediate action is required to safeguard subject safety. Administrative or minor changes (e.g., typographical errors, changes in Sponsor personnel, etc.) will be documented as revisions but may not need to be submitted as amendments unless required by the IRB. Any change in the Sponsor's monitoring staff, Clinical Trial Manager or Medical Monitor during the conduct of the study, will be reported to the Investigator.

During the course of the trial, the clinical site will allow monitoring by the Sponsor (Clinical Trial Manager or designee) to check compliance with the Protocol, regulations and guidelines, adequacy of the equipment and facilities, and satisfactory data collection.

1.7 Target Population

The target population of this study is generally healthy subjects ranging from 18-85 years with a normal salivary flow rate.

2. INVESTIGATIONAL PLAN

2.1 Overall Study Design and Plan

The purpose of this study is to evaluate the fluoride dose response of different dentifrice fluoride concentrations - 0, 250, 1100 and 2800 ppm fluoride as sodium monofluorophosphate (MFP) using an in-situ caries model.

The purpose of Period 5 is to evaluate the performance and sensitivity of the in-situ caries model to a SnF₂ toothpaste.

2.1.1 Primary Endpoints

The primary endpoint is the enamel fluoride uptake on Day 21 and the primary comparison between pastes with 0 and 2800ppm fluoride concentrations, and all other treatment comparisons and time points being of secondary interest. The secondary endpoints include % SMH recovery and SMH change (see 4.4).

2.1.2 Design Type

This is a randomized, four-treatment, 4-period crossover, double blind clinical trial. The target population is approximately 16 adult volunteers. During the course of the study, all subjects will be asked to voluntarily participate in a fifth period, not included as part of the crossover design. Those subjects willing to participate in Period 5 will sign an amended informed consent form and will all receive the same product during that period. Two to three days before the start of each treatment period the subjects will have their teeth cleaned to remove all accessible plaque and calculus and will be provided with a non-fluoride dentifrice to use until their next visit. At the beginning of each testing period, two gauze-covered 4 mm round partially demineralized human enamel specimens will be placed in the buccal flange area of the subject's mandibular partial denture. In addition, two gauze-covered 4 mm round partially demineralized human enamel specimens will be placed in the buccal surface of two posterior denture teeth of the same side of the partial denture. Once specimens are placed, subjects will wear their partial dentures twenty-four hours a day and use their assigned toothpaste twice daily, as instructed, until their next visit. Subjects will return at 7 and 14 days to have one specimen removed per visit, and again at 21 days to have the remaining two specimens removed. The specimen removal sequence will occur in a predetermined order starting with the anterior denture tooth specimen, posterior denture tooth specimen, and then the two buccal flange specimens. Following the 21-day specimen removal visit, the subjects will undergo a four- to five-day washout period followed by another cleaning and two- to three-day lead in period. This process will be repeated until all subjects have used all four test products. Changes in the mineral content of the enamel specimens will be assessed using the SMH. Enamel fluoride uptake (EFU) will be determined using the microdrill enamel biopsy technique.

Table 1. Study Schedule by Procedure Type and Visit

PROCEDURE	VISIT 1	VISIT 2, 7, 12, 17, 22	VISIT 3, 8, 13, 18, 23	VISIT 4, 9, 14, 19, 24	VISIT 5, 10, 15, 20, 25	VISIT 6, 11, 16, 21, 26
	SCREENING	PROPHY	BEGIN TREATMENT	7 DAY REMOVAL	14 DAY REMOVAL	END ¹ TREATMENT
Informed Consent	X					
Medical History Review	X	X	X	X	X	X
Demographics	X					
Oral Soft Tissue Exam	X	X	X			X
Oral Hard Tissue Exam	X	X (v2 only)				X (v21 and v26)
Salivary Flow	X					
Inclusion/Exclusion Criteria	X					
Continuance Criteria		X	X	X	X	X
Randomization			X (v3 only)			
Dental Prophylaxis		X				
Placement of specimens			X			
Issue washout toothpaste		X				
Return washout toothpaste			X			

Issue study products and diary			X			
Return study products and diary						X
General Comments	X	X	X	X	X	X
Adverse Events		X	X	X	X	X
Subject Accountability						X ¹ (v21 or 26)

¹ For those subjects continuing on Period 5, end of study activities will occur at Visit 26

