Each subject will receive an OST examination, answer continuation questions and have their medical history/medication information updated. Subjects will be asked to return the washout product they received at Visit 2 and will be given their randomized study product and diary for product use. Subjects will be instructed on the brushing method (see Appendix). The four enamel partially demineralized specimens will be placed in the buccal flange/posterior teeth areas on one side of the subject's mandibular partial denture. All subjects will be instructed to wear their partial denture containing the enamel specimens 24 hours a day except during the cleaning of their natural teeth (twice per day) and for short periods to rinse their mouth out with tap water after meals and snacks.

Visit 4 (7 Day Removal)

Seven (7) days following Visit 3, the subjects will return to the Institute and answer continuance criteria questions and update their medical history/medication information. One enamel specimen will be removed from anterior denture tooth site of their partial denture and the hollow will be filled with a temporary dental material (DentuSil™). The subjects will be told to continue using their assigned product as instructed.

Visit 5 (14 Day Removal)

Fourteen (14) days following Visit 3, the subjects will return to the Institute and answer continuance criteria questions and update their medical history/medication information. One enamel specimen will be removed from posterior denture tooth site of their partial denture and the hollow will be filled with a temporary dental material (DentuSil™). The subjects will be told to continue using their assigned product as instructed.

Visit 6 (End Treatment Period 1)

Twenty-one (21) days following Visit 3, the subjects will return to the Institute and receive an OST examination, answer continuance criteria questions and update their medical history/medication information. Subjects will be asked to return the study product and diary they received at Visit 3. The remaining two enamel specimens in the buccal flange site will be removed from their partial denture and the hollows will be filled with a temporary dental material (DentuSil)

Period 2, 3, 4 & 5

The procedures outlined above (Visit 2-6) will be repeated until each subject has used each of the four test products, followed by a 5th test product in Period 5. At Visit 21 (and also at Visit 26 for those subjects

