5. STATISTICAL PLAN

5.1 Statistical Methods

Efficacy Analyses

The mean % SMH recovery and SMH change will be calculated using the five sets of indentations within each enamel specimen. The mean fluoride uptake will be calculated using the four samples within each enamel specimen. The mean % SMH recovery, SMH change and mean fluoride uptake will be computed for each enamel specimen at the different time points (1 specimen for 7 and 14 days and 2 specimens for 21 days) within a subject; if a subject is missing an enamel specimen for the 21-day reading, the single available enamel specimen will be used. The treatments will be compared using analysis of variance models (ANOVA) or analysis of covariance (ANCOVA) suitable for a crossover study.

To assess for potential carryover effects on the primary endpoint, the models will include random effects for subject and fixed effects for study period, product and carryover term. If the carryover term is not significant at the 0.1 level ($p>0.1$) then the final crossover model will not include the carryover term.

A repeated measures crossover model will also be carried out to explore the treatment time effect. This model will include a random effect for subject and fixed effects for study period, product, treatment times (7, 14 and 21 days) and treatment time by product interaction. For SMH change, B (indentation length (μm) of sound enamel specimen at baseline) or D1 (indentation length (μm) after challenge) will be added as a covariate in the model. Additionally, the product by covariate interaction will also be assessed in this model. A 10% significance level will be used for all product comparison tests. No alpha-level adjustments for multiple comparisons adjustments will be applied.

If the data does not satisfy the normality criterion, log transformation or analogous nonparametric methods will be employed. Additional statistical techniques may also be applied in order to more fully understand the data.

The SnF_2 product used in Period 5 will be compared to the negative control treatment used in other periods using a paired t-test.

Safety Analyses

Adverse events reported during the study will be listed in the final report.

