5.4 Selection of Subjects

5.4.1 Intent-to Treat (ITT) Population

The subjects will be selected from the OHRI's IRB approved database of persons previously accepted into the partial denture panel (IRB #1110007150). Potential subjects will be screened to determine eligibility to participate in this study. Sixteen adult subjects, between the ages of 18 and 85 years, will be accepted and randomized in the study so at least 10 subjects can complete the study. The ITT population will include those subjects randomized and who had at least one exposure to product.

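### Removal day and specimen site are completely confounded, so the time main effect in section 5.1 cannot be read as an effect of treatment duration

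*Combined protocol and SAP*

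**What the plan says.** Section 2.1.2 places four specimens on one side of the mandibular partial denture: two in the buccal flange and two in the buccal surface of two posterior denture teeth. Removal "will occur in a predetermined order starting with the anterior denture tooth specimen, posterior denture tooth specimen, and then the two buccal flange specimens". Section 2.1.5 repeats this visit by visit:

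- Visit 4 (Day 7): "One enamel specimen will be removed from anterior denture tooth site of their partial denture".
- Visit 5 (Day 14): "One enamel specimen will be removed from posterior denture tooth site of their partial denture".
- Visit 6 (Day 21): "The remaining two enamel specimens in the buccal flange site will be removed from their partial denture".

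The same procedures apply in each later period. Nothing rotates or randomises sites over days, and nothing states that the sites are equivalent.

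On analysis, section 5.1 says: "A repeated measures crossover model will also be carried out to explore the treatment time effect". Besides a random subject effect, that model has "fixed effects for study period, product, treatment times (7, 14 and 21 days) and treatment time by product interaction". It has no term for site. Section 2.1.1 makes Day 21 enamel fluoride uptake (EFU), 0 versus 2800 ppm, the primary comparison and treats other time points as secondary.

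**The concern.** The time model has a stated purpose, and the layout cannot serve it. Day 14 minus Day 7 is one more week of use plus the difference between two tooth sites. Day 21 minus either earlier day is extra use plus the difference between flange and tooth. A finding that uptake or remineralisation rises, or levels off, between 7 and 21 days could come from site alone.

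The time-by-product terms are exposed in a narrower way. They can be read as duration effects only if site differences are the same for every product. Section 5.1 relies on that assumption without stating it.

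The protocol itself gives some reason to doubt that the sites are interchangeable. Subjects brush the biting surfaces of the back teeth and avoid the specimens, so the tooth specimens may lie closer to where paste is applied than the flange specimens do. This is inference; the documents contain no data by site.

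**Working it through.** The plan gives no figure for this analysis, and section 5.3 says the 16 subjects were chosen for logistical reasons. The check is therefore structural.

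**Inputs.** 16 subjects and the sequences ABCD, BDAC, CADB, DCBA (3.1.2), assumed 4 subjects per sequence; 4 crossover periods; 1, 1 and 2 specimens at Days 7, 14 and 21 (2.1.2). Rows: 16 × 4 × 4 = 256.

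**Day by site.**

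| | Anterior tooth site | Posterior tooth site | Flange |
|---|---|---|---|
| Day 7 | 64 | 0 | 0 |
| Day 14 | 0 | 64 | 0 |
| Day 21 | 0 | 0 | 128 |

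The indicator columns for day and for site are identical.

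**Rank.** With subject entered as fixed for the check, the 5.1 model has 1 + 15 + 3 + 3 + 2 + 6 = 30 columns (intercept, subject, period, product, time, product by time) and rank 30. Adding site leaves the rank at 30. Adding product by site as well also leaves it at 30. In degrees of freedom:

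| Layout | Time, ignoring site | Time, given site | Product × time, additive site | Product × time, given product × site |
|---|---|---|---|---|
| As planned | 2 | 0 | 6 | 0 |
| Two tooth sites alternated, Day 21 kept at flange | 2 | 1 | 6 | 3 |

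The B or D1 covariate for SMH change does not help. Both are measured before placement and carry no information about site.

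**Size of the bias.** If the expected response differs between two sites by x, the matching time contrast estimates (duration effect) + x. The error does not shrink with more subjects.

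**Illustration under assumed values.** Subject SD 1, residual SD 1, no duration effect, flange shifted from both tooth sites, two-sided 10% test of time (5.1 gives 10% for product comparisons; its use here is an assumption), 2000 simulated trials per row:

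| Flange shift (residual SD) | Mean estimate, Day 21 − Day 7 | Declared significant |
|---|---|---|
| 0 | 0.00 | 10% |
| 0.25 | 0.25 | 50% |
| 0.5 | 0.50 | 95% |
| 1.0 | 1.00 | 100% |

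A product contrast with true value 1.50 was estimated at about 1.50 in all four rows, so comparisons between products are not disturbed.

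**Precision if the tooth sites are alternated.** With subjects split a:b between the two removal orders and n = a + b, adding a tooth-position term multiplies the variance of Day 14 − Day 7 by n²/(4ab). At 8:8 this is 256/256 = 1.00. For n = 10, the minimum number of completers in 5.4.1:

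- 5:5, 100/100 = 1.00
- 4:6, 100/96 = 1.04
- 3:7, 100/84 = 1.19
- 2:8, 100/64 = 1.56, the worst split possible

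These count completers only. If the six dropouts all come from one order but each contributes one completed period, 1.56 falls to about 1.18 to 1.19. With two periods each it is about 1.06, and with three about 1.01.

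**The case against.** The strongest case against giving this much weight is that no stated objective depends on it. The study's purpose is fluoride dose response. The primary comparison is at one day and therefore one site type. Section 5.2 tests product differences at each time point and poses no hypothesis about change over time, and 5.1 introduces the time model as exploration. Harm arises only if a report reads the time effect as duration.

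All of that stands, and it limits the point to interpretation. It does not remove the point, because exploring the effect of time is the model's declared purpose and these data cannot provide it.

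Three narrower objections also have merit:

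- The Day 7 site is the more anterior of two posterior denture teeth, not a front tooth. Any label in the report should say so, or the contrast with Day 14 will look larger than it is.
- Alternating the tooth sites separates only Day 14 from Day 7, where both sites are of the same type. Flange versus tooth stays confounded with Day 21 versus earlier days, so the alternation is optional.
- The 1.56 variance ratio is a completers-only worst case. Section 2.2.4 allows data already gathered to be kept, so the likely cost is smaller.

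**Conclusion.** The concern holds. Removal day and site are the same variable in this design, and no model term or increase in sample size can separate them. The time main effect has no degrees of freedom left once site is allowed for. Product by time is interpretable as a duration effect only under an unstated assumption of no product-by-site interaction.

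The bias equals the site difference, whose size is unknown. Product comparisons at a fixed day are unbiased because all products share the same site on that day, although Day 21 results describe flange sites only. The df counts assume the full layout with 4 subjects per sequence; the aliasing itself does not depend on that. The plan should be changed, but the primary conclusion is not at risk.

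**What to change.** In section 5.1:

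1. Withdraw the time main effect as an estimate of treatment duration.
2. Report product differences at each day with the site named: Day 7, the more anterior of the two posterior denture teeth; Day 14, the more posterior; Day 21, buccal flange.
3. State that product by time is exploratory and assumes no product-by-site interaction.

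This costs almost nothing and keeps the product-by-time analysis and the primary endpoint as they are.

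**Optional.** Alternate across subjects which tooth specimen is removed at Day 7 and which at Day 14. Balance the two orders within treatment sequence (2 subjects per sequence per order, if sequences have 4 subjects each), keep each subject's order the same in all periods, and add tooth position to the model. Day 14 versus Day 7 then becomes estimable; Day 21 versus earlier days does not. The cost is a removal-order column in the sequence schedule, site tracking at two visits and one model term, with no extra specimens or visits.

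Rotating all four sites through all days would separate site from time fully. It would also cut the flange share of Day 21 specimens from 100% to 50% and so alter what the primary endpoint measures. That trade-off is for the sponsor and is not recommended here.
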